11.8. Interim Analyses

No formal interim analysis is planned.

11.9. Data and Safety Monitoring Board

Two external reviewers (1 neurologist and 1 neuroradiologist), who are not involved in the study conduct and are blinded to the treatment assignments, will assess all cases of ICH. The neuroradiologist will review all CT or MR scans (independent to the Investigator at site), and classify any ICH findings according to the ECASS morphologic definitions.

The neurologist will assess whether neurologic deterioration is due to ICH, or other causes.

Dose Escalation Safety Data Review:

Blinded clinical (bleeding and other AEs) and safety laboratory data of each completed dose level will be reviewed prior to escalation to the next dose level. The dose escalation decision will be made based on this data review. Participants in the dose escalation safety data review meetings are the following: Clinical Study Leader, Medical Monitors from the Sponsor and PAREXEL, external reviewers for ICH, Clinical Study Manager, and Statistician from the Sponsor.

11.10. Sample Size Determination

The sample size for this study is not based on statistical power calculations. The number of subjects at each dose level is considered sufficient to achieve the primary objective of this study.

At least 8 subjects each will be enrolled in the first 2 cohorts. An additional expansion cohort of 8 subjects may be added during the first 2 cohorts if additional information is needed in order to move forward with the last 3 cohorts. At least 16 subjects each will be enrolled in the last 3 cohorts: 12 of which will be randomized to active treatment, and 4 to placebo treatment. A stopping rule of sICH is predefined: 2 cases of sICH in 12 active-treated subjects per dose level, or 4 cases of sICH in active-treated subjects cumulatively across dose levels. This sample size and stopping rule are determined in consideration of sICH observation and dose escalation criteria in small dose cohort safety studies conducted with tissue plasminogen activator.^{3,4} The incidence of sICH observed is about 16% per dose level in these studies. The sample size and stopping rule of sICH in current study are designed to prevent a greater incidence of sICH than observed with tissue plasminogen activator in small dose cohort safety studies.

12. DATA INTEGRITY AND QUALITY ASSURANCE

The Investigator/investigational site will permit study-related monitoring, audits, IRB/EC review and regulatory inspections by providing direct access to source data/documents. Direct access includes permission to examine, analyze, verify, and reproduce any records and reports that are important to the evaluation of a clinical study.

12.1. Monitoring and Inspections

The DSPD and CRO monitors and regulatory authority inspectors are responsible for contacting and visiting the Investigator for the purpose of inspecting the facilities and, upon request, inspecting the various records of the study (eg, eCRFs, source data, and other pertinent documents).

The monitor is responsible for visiting site(s) at regular intervals throughout the study to verify adherence to the protocol; completeness, accuracy, and consistency of the data; and adherence to International Conference on Harmonisation GCP and local regulations on the conduct of clinical research. The monitor is responsible for inspecting the eCRFs and ensuring completeness of the study essential documents. The monitor should have access to subject medical records and other study-related records needed to verify the entries on the eCRFs.

The monitor will communicate deviations from the protocol, SOPs, GCP and applicable regulations to the Investigator and will ensure that appropriate action designed to prevent recurrence of the detected deviations is taken and documented.

The Investigator agrees to cooperate with the monitor to ensure that any problems detected in the course of these monitoring visits are addressed and documented.

In accordance with International Conference on Harmonisation GCP and the Sponsor's audit plans, this study may be selected for audit by representatives from the Sponsor. Inspection of site facilities (eg, pharmacy, drug storage areas, laboratories, etc) and review of study-related records will occur in order to evaluate the study conduct and compliance with the protocol, International Conference on Harmonisation GCP, and applicable regulatory requirements.

12.2. Data Collection

The eCRF completion should be kept current to enable the monitor to review the subject's status throughout the course of the study. The eCRF will be completed, reviewed, and signed off or e-signed by the Investigator.

The Investigator e-signs the eCRF according to the study data flow.

Any data recorded on the study eCRF will be collected and included in the database according to CDISC standards and subjected to the same procedures as other data.

12.3. Data Management

Each subject will be identified in the database by a unique subject identifier as defined by the Sponsor.

To ensure the quality of clinical data across all subjects and sites, a Clinical Data Management review will be performed on subject data according to specifications given to DSPD and/or the CRO. Data will be vetted both electronically and manually for eCRFs the data will be electronically vetted by programmed data rules within the application. Queries generated by rules and raised by reviewers will be generated within the Electronic Data Capture (EDC) application. During this review, subject data will be checked for consistency, omissions, and any apparent discrepancies. To resolve any questions arising from the Clinical/Data Management review process, queries will be raised and resolved within the EDC application.

Data received from external sources such as central labs will be reconciled to the clinical database.

Serious adverse events in the clinical database will be reconciled with the safety database.

All adverse events and medical history will be coded using MedDRA. Concomitant medications will be coded using the current WHO Drug Dictionary.

12.4. Study Documentation and Storage

The Investigator will maintain a Signature List of appropriately qualified persons to whom he/she has delegated study duties. All persons authorized to make entries and/or corrections on eCRFs will be included on the Signature List.

Source documents are original documents, data, and records from which the subject's eCRF data are obtained. These include but are not limited to hospital records, clinical and office charts, laboratory and pharmacy records, diaries, microfiches, X-rays, and correspondence.

The Investigator and study staff are responsible for maintaining a comprehensive and centralized filing system (Trial Master File) of all study-related (essential) documentation, suitable for inspection at any time by representatives from the Sponsor and/or applicable regulatory authorities. Essential documents include:

- Subject files containing completed eCRFs, informed consents, and supporting copies of source documentation (if kept).
- Study files containing the protocol with all amendments, Investigator's Brochure, copies of relevant essential documents required prior to commencing a clinical study, and all correspondence to and from the IRB/EC and the Sponsor.
- Records related to the Investigational Product(s) including acknowledgment of receipt at site, accountability records and final reconciliation and applicable correspondence.

In addition, all original source documents supporting entries in the eCRFs must be maintained and be readily available.

All essential documentation will be retained by the Investigator until at least 2 years after the last approval of a marketing application in an International Conference on Harmonisation region and until there are no pending or contemplated marketing

applications in an International Conference on Harmonisation region or at least 2 years have lapsed since the formal discontinuation of clinical development of the investigational product. These documents should be retained for a longer period, however, if required by the applicable regulatory requirements or by an agreement with the Sponsor. It is the responsibility of the Sponsor to inform the Investigator/institution as to when these documents no longer need to be retained.

No study document should be destroyed without prior written agreement between Sponsor and the Investigator. Should the Investigator wish to assign the study records to another party or move them to another location, he/she must notify Sponsor in writing of the new responsible person and/or the new location.

12.5. Record Keeping

Records of subjects, source documents, monitoring visit logs, data correction forms, eCRFs, inventory of study product, regulatory documents (eg, protocol and amendments, IRB/EC correspondence and approvals, approved and signed ICFs, Investigator's Agreement, clinical supplies receipts, distribution and return records), and other Sponsor correspondence pertaining to the study must be kept in appropriate study files at the site. Source documents include all recordings and observations or notations of clinical activities and all reports and records necessary for the evaluation and reconstruction of the clinical study. These records will be retained in a secure file for the period required by the institution or site policy. Prior to transfer or destruction of these records, the Sponsor must be notified in writing and be given the opportunity to further store such records.

13. FINANCING AND INSURANCE

13.1. Finances

Prior to starting the study, the Principal Investigator and/or institution will sign a clinical study agreement with DSPD and/or the CRO. This agreement will include the financial information agreed upon by the parties.

13.2. Reimbursement, Indemnity, and Insurance

Reimbursement, indemnity, and insurance shall be addressed in a separate agreement on terms agreed upon by the parties.

14. PUBLICATION POLICY

15. STUDY ADMINISTRATIVE INFORMATION

15.1. Protocol Amendments

Any amendments to the study protocol that seem to be appropriate as the study progresses will be communicated to the Investigator by the Sponsor. All protocol amendments will undergo the same review and approval process as the original protocol. A protocol amendment may be implemented after it has been approved by the IRB/EC, unless immediate implementation of the change is necessary for subject safety. In this case, the situation must be documented and reported to the IRB/EC within five working days. The Sponsor will assure the timely submission of amendments to regulatory authorities.

17. APPENDICES

17.1. Additional Information on Investigational Products

Not applicable.

17.2. Instructions for Specimen Collection, Storage and Shipment

17.2.1. Sample Handling Instructions for Pharmacogenomic Samples

The detail instructions for collection, storage, handling, and shipping of blood samples for pharmacogenomics samples will be provided separately in a laboratory manual.

17.2.2. Collection, Storage, Handling, and Shipping of Blood Samples for PD Analysis

The detail instructions for collection, storage, handling, and shipping of blood samples for PD analysis will be provided separately in a laboratory manual.

17.2.3. Collection, Storage, Handling, and Shipping for Sample Analysis of Plasma DS-1040b

The detail instructions for collection, storage, handling, and shipping of blood samples for PK analysis will be provided separately in a laboratory manual.

17.2.4. Collection, Storage, Handling, and Shipping for Sample Analysis of Urinary DS-1040b

The detail instructions for collection, storage, handling, and shipping of urine samples for PK analysis will be provided separately in a laboratory manual.

17.3. Listing of Laboratory Assays

The total blood volume that will be taken from each subject is 176.7 mL.

Test	Volume per test (mL)	Number of Timepoints per Subject	Total Volume (mL)
Baseline			
Serum chemistry, follicle stimulating hormone, serum pregnancy	8.5	1	8.5
Hematology	4	1	4
PT/INR/aPTT/fibrinogen	2.7	1	2.7
Other visits:			
Genotyping (optional)	4	1	4
Serum chemistry (including PT/INR/fibrinogen when scheduled at the same time)	8.5	4	34
Hematology	4	4	16
PT/INR/aPTT/fibrinogen/D-dimer (Local laboratory)	2.7	3	8.1
PT/INR/aPTT (Central laboratory – Medpace, Inc.)	2.7	6	16.2
D-dimer (Central laboratory – Medpace)	2.7	6	16.2
Total TAFIa activity (Central laboratory)	2.7	6	16.2
Clot lysis (Central laboratory)	2.7	6	16.2
TAFI antigen (Central laboratory)	2.7	3	8.1
PK	2	9	18
Total			168.2
aPTT = activated partial thromboplastin time; HIV = human immunodeficiency virus; INR = International Normalized Ratio; PK = pharmacokinetic; PT = prothrombin time; TAFIa = thrombin-activatable fibrinolysis inhibitor.			

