The change in coagulation parameters prothrombin time (PT), internal normalized ratio (INR), activated partial thromboplastin time (aPTT), and fibrinogen from baseline were minor and not clinically significant; no clear dose related trends were noted. There was no clinically significant effect on platelet aggregation (performed with 10 μ M adenosine 5'-diphosphate and 0.5 mM arachidonic acid) at any dose level. In Part 1, an increase in bleeding time of 40% to 66% was observed on Day 1 at the end of infusion compared with Day -1 following DS-1040b doses of 3 mg, 6 mg, and 12 mg. All bleeding time values in Part 1 remained within the normal range (less than 10 minutes), and these changes in bleeding time were not considered significant. The bleeding time in Part 2 and Part 3 did not show any DS-1040b dose related trend. There were no clinically significant changes on any other safety laboratory parameters.

Plasma exposure of DS-1040a, a free form of DS-1040b, increased proportionally with increases in dose. Higher exposure levels were observed in elderly subjects compared

with young subjects, which is due to prolonged systemic elimination. The mean half-life ($t_{1/2}$) in elderly subjects was longer than that in young subjects at corresponding doses. With 24-hour continuous infusion, by 12 hours after the end of infusion, plasma drug concentrations decreased to < 10% of the end-of-infusion concentration.

DS-1040b administration resulted in a dose-dependent decrease in TAFIa activity and 50% clot lysis time. A drug-related increase of D-dimer was also observed without clear dose dependency in healthy subjects. There were no changes in the level of TAFI antigen.

In a Phase 1, open-label, single-dose, drug-drug interaction study (DS1040-E-102), the safety and tolerability of a single, IV dose of DS-1040b was assessed in healthy subjects after 5 days of aspirin treatment. A total of 18 subjects were enrolled in this study. Each subject received a loading dose of 300 mg aspirin on the morning of Day 1 followed by a daily dose of 75 mg aspirin on Days 2, 3, 4, and 5. On the morning of Day 5, the daily dose of aspirin was followed immediately by a 6-mg IV infusion of DS-1040b over 0.5 hours.

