5. TREATMENTS ADMINISTERED

5.1. Investigational Products

The Investigator must ensure that the investigational product will be used only in accordance with the protocol.

DS-1040b Injection 10 mg/10 mL is transferred into IV infusion solution (0.9% Sodium Chloride Injection, USP), as shown in Table 5.1. The placebo for DS-1040b will be 0.9% Sodium Chloride Injection, USP. In order to maintain the blind, placebo solution will be administered in the same manner as the DS-1040b IV solution in the respective cohort. The detailed procedures for drug preparation will be provided separately in pharmacy manual.

DS-1040b IV solution will be administered as an initial 0.5-hour infusion (25% of the total dose) followed by a 5.5-hour continuous IV infusion (75% of the total dose). In each cohort, 8 to 16 subjects will be randomized in a ratio of 3:1 (active:placebo). The assignment of either active or placebo will be blinded to subjects, Investigators, and the CRO staff.

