9.5. Clinical Laboratory Evaluations

The following clinical laboratory tests will be performed:

- Hematology variables, including but not limited to red blood cell count, hemoglobin, hematocrit, platelet count, and white blood cell count with 5-part differential, including absolute neutrophil count
- Serum chemistry variables, including but not limited to calcium, glucose, serum creatinine, blood urea nitrogen, aspartate aminotransferase, alanine aminotransferase, alkaline phosphatase, total and direct bilirubin, sodium, potassium, bicarbonate, and chloride
- Urinalysis variables, including but not limited to protein, glucose, blood, microscopy assessments, and specific gravity
- Coagulation: INR, PT, aPTT, and fibrinogen
- Serum pregnancy test (for women of childbearing potential)

All laboratory values must be appraised by the Investigator as to clinical significance. All abnormal laboratory values considered clinically significant by the Investigator must be recorded in the adverse event page of the eCRF. Abnormal laboratory values occurring during the clinical study will be followed until repeat test results return to normal (or baseline), stabilize, or are no longer clinically significant.

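### Section 17.3 puts D-dimer, a marker the protocol says the drug raises, on a local-laboratory panel after dosing; this is an avoidable risk of partial unblinding of the Investigator, of unknown size.

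*Combined protocol and SAP*

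**What the plan says.** Section 17.3, under the part of the table for visits other than baseline, lists "PT/INR/aPTT/fibrinogen/D-dimer (Local laboratory" at 3 timepoints of 2.7 mL. The baseline coagulation row, "PT/INR/aPTT/fibrinogen 2.7 1 2.7", has no D-dimer. The same table also sends D-dimer to the central laboratory at 6 timepoints. The remaining PD markers have central rows only, for example "Total TAFIa activity (Central laboratory".

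Sections 6 and 8.2 treat D-dimer as a PD sample, drawn predose and at 0.5, 6, 12, 24 and 48 hours. The safety panel in Section 9.5 reads "Coagulation: INR, PT, aPTT, and fibrinogen", without D-dimer.

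On the drug effect, Section 1.1.1.5 says: "A drug-related increase of D-dimer was also observed without clear dose dependency in healthy subjects". The same section describes the changes in PT, INR, aPTT and fibrinogen as minor and without a clear dose trend.

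On blinding, Section 5.1 says: "The assignment of either active or placebo will be blinded to subjects, Investigators, and the CRO staff". Section 9.5 says: "All laboratory values must be appraised by the Investigator as to clinical significance"; Section 9.1 repeats the duty. No section masks, delays or withholds a local D-dimer result.

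**The concern.** Of the analytes on the local row, D-dimer is the only one for which the protocol reports a drug effect. A result from the site's own laboratory would normally return to the site, where the blinded Investigator has a duty to appraise laboratory values.

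The same Investigator judges the seriousness, severity and causality of adverse events (Section 9.1), assesses all bleeding events, and documents clinical deterioration as part of the sICH definition (Section 9.9.1). No independent rater is named for NIHSS or mRS. Safety is the primary objective, and sICH and non-ICH major bleeding both feed the stopping rules in Section 3.1.6. A hint about allocation could therefore colour judgements that matter.

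There is a second, smaller route. A D-dimer value judged clinically significant would have to be recorded as an adverse event, and Section 9.2.4 counts as related an event predicted by known pharmacology. An expected PD effect could then appear in the safety tables.

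**Working it through.** **1. The plan's own figures.** Local row: 3 × 2.7 mL = 8.1 mL, as printed. The 13 rows of Section 17.3 sum to 8.5 + 4 + 2.7 + 4 + 34 + 16 + 8.1 + 16.2 + 16.2 + 16.2 + 16.2 + 8.1 + 18 = 168.2 mL, as printed in the total row. The sentence above the table says 176.7 mL, which is 8.5 mL more; that is a separate discrepancy.

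**2. Is the local test a duplicate?** Scheduled D-dimer times (Sections 6.1 to 6.3 and 8.2) are predose, 0.5, 6, 12, 24 and 48 h, so 6. The central D-dimer row also has 6. The central assay covers every scheduled time, and the 3 local results add no scheduled PD data.

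**3. When are the local draws?** The table gives no hours. The schedule has one predose time, so if the 3 local draws fall at distinct scheduled times, at most 1 is predose and at least 3 − 1 = 2 are postdose.

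The hours cannot be fixed more closely:
- Section 6 has chemistry at 24 and 48 h after dosing. The row "Serum chemistry (including PT/INR/fibrinogen when scheduled at the same time" suggests coagulation shares that draw. Then 5 postdose coagulation times − 2 = 3, which would be 0.5, 6 and 12 h.
- Section 17.3 itself lists chemistry at 4 timepoints outside baseline. On that count 5 − 4 = 1, which does not match the row.
- The heading for other visits does not mean postdose. The 6 central D-dimer draws include predose, and so do the 3 TAFI antigen draws (predose, 6 and 24 h in Section 6).

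**4. How much could a result reveal?** The documents give no effect size, no rates and no data in stroke subjects, so the rates below are assumptions. With 3:1 randomization the prior probability of active is 0.75. Let a and p be the probability of a visible rise on active and on placebo:

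- P(active | rise) = 0.75a / (0.75a + 0.25p)
- P(active | no rise) = 0.75(1 − a) / [0.75(1 − a) + 0.25(1 − p)]

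| Assumed a, p | After a rise | After no rise |
|---|---|---|
| 50%, 40% | 0.375/0.475 = 79% | 0.375/0.525 = 71% |
| 60%, 30% | 0.450/0.525 = 86% | 0.300/0.475 = 63% |
| 80%, 20% | 0.600/0.650 = 92% | 0.150/0.350 = 43% |

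With a weak signal the Investigator learns almost nothing; with a strong one, a good deal. The documents do not say which applies.

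**5. Which assessments are exposed?**

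| Assessment | Blinded external review? |
|---|---|
| ICH findings and their role in deterioration | Yes, two reviewers (9.9.1, 11.9) |
| Recanalization | Yes, neuroradiologist (8.2) |
| Adverse event severity and causality | No (9.1) |
| Non-ICH bleeding | No (9.9.1) |
| Investigator's record of deterioration | No, but the external neurologist judges its cause |
| NIHSS, mRS | No rater named (9.9.2, 10) |

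**The case against.** The strongest reply is that this may be a drafting slip. The local D-dimer appears only in a blood-volume table that has other faults: two different totals, chemistry at 4 timepoints against 2 in Section 6, and 9 PK draws against 10 in Section 8.1. The table of contents groups D-dimer with total TAFIa activity as a PD specimen, and sample handling is left to a laboratory manual that is not among the documents. The appraisal sentence in Section 9.5 closes a list that omits D-dimer. This stands in part: that the Investigator sees the result is an inference. It is a reasonable one, because Section 9.1 states the duty generally and no masking is described. If the row is a slip, the same correction removes it.

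A second reply is that much is already protected. ICH and recanalization have blinded external readers, non-ICH major bleeding requires a stated hemoglobin or hematocrit drop, and the analyses are descriptive. This also stands, and it limits the exposure to the assessments without central review.

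A third is that the documents do not say why the local test was listed or how fast central results return, so a clinical use cannot be ruled out. That is a reason to allow an exception for documented clinical need.

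The lack of clear dose dependency does not answer the point: what is masked is active versus placebo, not the dose level of the cohort.

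**Conclusion.** The point holds as an avoidable risk of partial unblinding. Three local D-dimer results per subject are listed, at least 2 of them postdose, for a marker with a reported drug-related rise. They duplicate the central schedule and fall outside the Section 9.5 safety panel. The risk bears on adverse event severity and causality, non-ICH bleeding, Investigator-documented deterioration, and NIHSS and mRS if the Investigator rates them.

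A reader might infer more than the documents support:
- *That the blind is broken.* The rise was seen in healthy subjects, with no size given, and background variation in stroke could weaken it. The 79% to 92% range rests wholly on assumed rates.
- *That the draws fall at 0.5, 6 and 12 h, during and just after the infusion.* This takes the chemistry count from Section 6 and ignores the different count in Section 17.3.
- *That the sICH stopping rule is compromised.* Two blinded external reviewers assess every ICH case. Only the Investigator's record of deterioration is exposed.

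The conclusion assumes that local results reach the Investigator and that the 3 draws fall at distinct scheduled times. It is worth correcting because the correction is cheap, not because harm has been shown.

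**What to change.** Delete D-dimer from the local-laboratory row in Section 17.3, so that the local panel matches Section 9.5 (PT, INR, aPTT, fibrinogen) and agrees with the PD status of D-dimer in Section 8.2.

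Add one sentence to Section 8.2: postdose PD markers (D-dimer, TAFIa activity, clot lysis, TAFI antigen) are measured centrally and are not released to blinded site or CRO staff before database lock, except for documented clinical need.

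The cost is one table row and one sentence. All 6 scheduled central D-dimer measurements and the Section 9.5 panel are unchanged. The downside is that sites lose a routine local D-dimer result that the protocol's safety panel does not require; the exception keeps access open where a clinical need is documented.
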